The number of days to reach control during the hospital stay statistically were not different between groups (by protocol 4.9 ± 2.2 days vs 4.7 ± 2.4 days, $p = 0.553$, by intention to treat 4.9 ± 2.1 days vs 4.7 ± 2.3 days, $p = 0.445$).

SAFETY RESULTS

Safety was evaluated with episodes of hypoglycemia and complications associated with diabetes. In the "physiological" group it was observed that 15 (41.6%) patients had at least one event of hypoglycemia during their entire stay; On the other hand, in the traditional group 15 (38.4%) presented at least one event of hypoglycemia (per protocol, RR: 1.11, 95% CI: 0.62 to 1.97, $p = 0.729$; intention to treat, RR = 1.08, 95% CI: 0.62 to 1.89, $p = 0.777$). The presence of more than 2 hypoglycemic events during their hospitalization was observed in 8 (22.2%) patients of the "physiological" group and in 2 (5.1%) patients of the traditional group (per protocol, RR = 7.75, 95% CI: 1.02 a 59.13, $p = 0.021$; by intention to treat, RR: 4.33, 95% CI: 0.98 to 19.07, $p = 0.041$).

In the analysis by protocol, the rate of the number of total events / patients with hypoglycemia in the "physiological" group was 2.4 ± 1.3 events / patient, while in the traditional group it was 1.6 ± 0.7 events / patient ($p = 0.129$) ; in the intention-to-treat analysis in the "physiological" group it was 2.5 ± 1.6 events / patient, whereas in the traditional group it was 1.7 ± 0.9 events / patient ($p = 0.182$).

Thirty-eight hypoglycemic events were found in the "physiological" group and 26 hypoglycemic events in the traditional group; of which, 36 were mild hypoglycemia in the "physiological" group and 24 events in the traditional group (RR per protocol: 1.02, 95% CI: 0.91 to 1.19, $p = 1.0$; RR by intention to treat: 1.03, 95% CI: 0.90 to 1.17, $p = 1.0$).

Regarding the complications associated with diabetes, soft tissue infection was the most frequent, one patient had pneumonia, one acute renal failure, one acute

respiratory failure, and no patient presented bacteremia, diabetic ketoacidosis or hyperosmolar state. Two of the patients included in the study died from complications not associated with hypoglycemia, one in the physiological group secondary to progression of the infectious process, sepsis and septic shock, and one in the group Traditionally associated with acute respiratory failure.

SECONDARY RESULTS

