There was a significant difference in the sustained control of blood glucose that was reported in 20 (55.6%) of the cases in the physiological group compared to 30 (76.9%) of the traditional group (per protocol, RR: 0.74, 95% CI: 0.58 to 0.94, $p = 0.009$; by intention to treat, RR: 0.72, 95% CI: 0.51 to 1.01, $p = 0.049$).

The causes of failure of the sustained control were discharge before control in goals, progress to critical state, death before glycemic control, poor adherence to the protocol and suspension for sustained hypoglycemia. With the "physiological" scheme it was necessary to suspend or change by another scheme in 8 (22.2%) patients, in comparison with the traditional scheme where only the scheme was suspended or changed in 1 (2.6%) patient (by intention to treat, RR: 8.67, 95% CI: 1.14 to 65.92, $p = 0.011$). There were no adverse effects to the use of insulin in both groups.

OTHER RESULTS

If the suspension of the scheme is considered for sustained hypoglycemia of 8 patients in the physiological group vs 1 patient in the control group, a risk ratio of 8.67 (95% CI: 1.14 to 65.9) and a number necessary to harm of 5.09 was calculated (95% CI: 2.93 to 19.23) patients with the physiological scheme to produce 1 event of hypoglycemia.

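### The NNH of 5.09 is correctly computed for suspensions of the insulin scheme, but its closing clause labels it as patients per hypoglycemia event

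*Combined protocol and SAP*

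**What the plan says.** The sentence under OTHER RESULTS opens by naming its input: "If the suspension of the scheme is considered for sustained hypoglycemia of 8 patients in the physiological group vs 1 patient", the second count being the traditional arm. It gives a risk ratio of 8.67 and then a "number necessary to harm of 5.09 was calculated (95% CI: 2.93 to 19.23) patients with the physiological scheme to produce 1 event of hypoglycemia".

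The 8 and the 1 come from SECONDARY RESULTS, where under the physiological scheme "it was necessary to suspend or change by another scheme in 8 (22.2%) patients", against 1 (2.6%) under the traditional scheme.

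SAFETY RESULTS reports hypoglycemia itself in three ways:

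- At least one event: "15 (41.6%) patients had at least one event of hypoglycemia during their entire stay" in the physiological group, while "in the traditional group 15 (38.4%) presented at least one event of hypoglycemia".
- Repeated events: "The presence of more than 2 hypoglycemic events during their hospitalization was observed in 8 (22.2%) patients" under the physiological scheme, against 2 (5.1%) under the traditional one.
- Total events: 38 in the physiological group and "26 hypoglycemic events in the traditional group".

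STATISTICAL ANALYSIS plans the RR, RAR (read here as absolute risk reduction), RRR and NNT, by protocol and by intention to treat. SAMPLE SIZE rests on a 25% difference in the hypoglycemia rate.

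**The concern.** The sentence starts with one outcome and ends with another. Its counts are patients whose scheme was suspended. Its conclusion is about hypoglycemia events. The report's own figures show that these differ: 15 patients in each arm had at least one event, but only 8 and 1 had the scheme suspended or changed.

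The rules for managing hypoglycemia also separate them. After a first event the insulin dose is cut by 20%; the regimen is suspended if more than one further event follows that cut. The diet section adds suspension for episodes linked to unfinished meals. In each case suspension is a treatment decision that follows hypoglycemia, taken in an unblinded trial.

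The label sits on a harm conclusion about the outcome used to size the trial. A reader who lifts the NNH with its closing clause would report that about five patients on the physiological scheme produce one extra hypoglycemia event, with an interval that excludes no harm. It is also the only derived absolute-effect measure (risk difference or NNH) that the report attaches to hypoglycemia.

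**Working it through.** **Inputs.** The intention-to-treat denominators are 36 physiological and 39 traditional (PATIENTS OF THE STUDY). The numerators are those listed above.

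**Formulas.** Risk difference RD = p1 - p2, with SE = sqrt[p1(1 - p1)/n1 + p2(1 - p2)/n2] and 95% limits RD ± 1.96 SE. NNH = 1/RD, with limits that are the reciprocals of the RD limits. The RR interval is on the log scale, with SE = sqrt(1/a - 1/n1 + 1/b - 1/n2).

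**Step 1: reproduce the stated figure from suspensions.**

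- RD = 8/36 - 1/39 = 0.2222 - 0.0256 = 0.1966; SE = 0.0738; limits 0.0520 to 0.3412.
- NNH = 1/0.1966 = 5.09; limits 1/0.3412 = 2.93 and 1/0.0520 = 19.23.
- RR = 0.2222/0.0256 = 8.67 (1.14 to 65.92).

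Every reported value matches.

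**Step 2: apply the same formulas to the hypoglycemia counts (intention to treat).**

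| Outcome | Counts | RD (95% CI) | NNH | RR (95% CI) |
|---|---|---|---|---|
| Suspension | 8/36 v 1/39 | 0.197 (0.052 to 0.341) | 5.09 (2.93 to 19.23) | 8.67 (1.14 to 65.92) |
| At least one event | 15/36 v 15/39 | 0.032 (-0.190 to 0.254) | 31.2, interval includes no harm | 1.08 (0.62 to 1.89) |
| More than 2 events | 8/36 v 2/39 | 0.171 (0.019 to 0.323) | 5.85 (3.09 to 54.0) | 4.33 (0.98 to 19.07) |

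Both hypoglycemia RRs match SAFETY RESULTS, so the counts are the ones the report used. For at least one event, the RD limits correspond to an NNH of 1/0.254 = 3.9 at one end, through no effect, to an NNT of 1/0.190 = 5.3 at the other.

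**Step 3: total events.** 38/36 - 26/39 = 1.056 - 0.667 = 0.389 extra events per patient, or one extra event per 1/0.389 = 2.57 patients. A Poisson interval for the difference is -0.03 to 0.81; it ignores clustering of events within patients.

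**Step 4: per-protocol variants.** The report prints per-protocol RRs but not the counts, so the counts here are inferred. For at least one event, 13/28 v 13/31 reproduces RR 1.11 (0.62 to 1.97) and gives NNH 22.3. For more than 2 events, 7/28 v 1/31 reproduces RR 7.75 (1.02 to 59.13) and gives NNH 4.59 (2.57 to 21.9).

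None of these hypoglycemia figures gives 5.09 (2.93 to 19.23). Only suspensions on the intention-to-treat denominators do.

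**The case against.** The best defence is that the closing clause is shorthand. The sentence opens with suspension for sustained hypoglycemia, so a careful reader can take the last words as the event just defined. Suspension is itself a consequence of hypoglycemia in this trial, and the nearest hypoglycemia outcome, more than 2 events, gives a similar NNH (5.9 against 5.09). The disclosure and the similarity both stand, and they limit the weight of the point. The shorthand does not rescue the wording: a first event leads to a dose cut, so a single event is not a suspension. The upper NNH limit also differs materially, 54 against 19.

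Several stronger readings are tempting, and the documents do not support them:

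- *The NNH is miscalculated or its basis concealed.* It reproduces exactly, and its basis opens the same sentence.
- *The report offers no other absolute figure for hypoglycemia.* SAFETY RESULTS prints the risks by arm, 41.6% v 38.4% and 22.2% v 5.1%, and reports the any-event comparison plainly as null (RR 1.08, p = 0.777).
- *The label inflates harm.* That depends on the meaning given to an event. Against 31 or 5.9 the stated figure overstates harm; against 2.6 it understates it.
- *There is no hypoglycemia signal once the label is corrected.* More than 2 events favours the traditional scheme, with p = 0.041 by intention to treat and p = 0.021 per protocol.
- *The suspended patients are known to differ from those with more than 2 events.* The per-protocol counts suggest it: 28 - 20 = 8 physiological patients did not complete to discharge, while only 7 per-protocol patients appear to have had more than 2 events. But the report never says that those 8 are the suspended patients, and the point does not need it.

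**Conclusion.** The point holds as a labelling error in one clause. The NNH of 5.09 (2.93 to 19.23) and the RR of 8.67 are correct for suspension of the scheme and should stay. They are not figures for one hypoglycemia event. For the plainest patient-level reading, at least one event, the NNH is about 31 and the data are compatible with no harm. For more than 2 events it is 5.9, on borderline evidence: the intention-to-treat RD interval excludes zero, but the RR interval (0.98 to 19.07) includes 1.

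This is a minor reporting correction. A reader might infer a flaw in the design or in the main hypoglycemia comparison, but no planned analysis, test or sample-size figure changes.

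The conclusion rests on the printed counts and on large-sample intervals, which are approximate with so few events. It also takes the report's word that the suspensions were for sustained hypoglycemia; SECONDARY RESULTS counts schemes suspended or changed without giving a reason for each patient.

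**What to change.** Replace the closing clause with: *to produce 1 additional suspension of the scheme for sustained hypoglycemia*. Beside it, report the intention-to-treat risk differences:

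- At least one event: 3.2 points (-19.0 to 25.4), NNH about 31, interval includes no harm.
- More than 2 events: 17.1 points (1.9 to 32.3), NNH 5.9 (3.1 to 54), with the intention-to-treat RR of 4.33 (0.98 to 19.07), p = 0.041, and the per-protocol RR of 7.75 (1.02 to 59.13), p = 0.021.

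The rewording alone removes the error. The risk differences supply absolute measures of the kind the analysis plan already names. The cost is one clause and two calculations from printed counts. What the report gives up is an NNH with a clear interval worded as hypoglycemia; the similar-sized figure for more than 2 events remains, with its wider interval.
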